16.6. OTHER SAFETY ASSESSMENTS

Handling of missing data for the following assessments is presented in Section 7.1.

16.6.1. YOUNG MANIA RATING SCALE (YMRS)

The YMRS is an 11-item, clinician-administered mania rating scale with established reliability, validity, and sensitivity that was designed to assess the severity of manic symptoms. Four of the YMRS items are rated on a 0 to 8 scale, with the remaining 7 items rated on a 0 to 4 scale. The total score is the sum of all 11 items and ranges from 0 to 60. The total score is appropriate both for assessing baseline severity of manic symptoms and for assessing treatment-emergent manic symptoms in subjects with Bipolar I or Bipolar II Disorder with

Document: ...\ITI\ITI-007\MYA11638\Biostatistics\Documentation\SAP\ITI-007-404 SAP Final V1.0 12JUN2019.docx Author: Version Number:1.0

Version Date: 12JUN2019

Page 40 of 53

depression. It will be completed by the investigator or an expert site-based rater.

The observed and change from baseline in YMRS total score will be summarized by treatment and visit.

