4 STUDY DESIGN

This is a Phase 3, randomized, double-blind, placebo-controlled, multi-center study to evaluate the efficacy and safety of lumateperone monotherapy in the treatment of patients with major depressive episodes associated with Bipolar I or Bipolar II Disorder (Bipolar Depression). The study consists of the following periods: Screening Period, double-blind On-treatment Period, and Safety Follow-up Period.

Screening Period (2 Weeks)

Potential patients will be evaluated during a Screening Period lasting up to 2 weeks, to ensure sufficient washout of restricted medications. Extension to the screening period may be approved by the Sponsor or representative in extenuating circumstances related to the patient or caregiver.

After obtaining written informed consent, diagnostic interviews and physical examinations will be conducted, vital signs and ECGs will be assessed, and blood samples for laboratory assessments will be collected. Patients considered potentially eligible for participation will be required to discontinue their current antidepressant treatment and/or other psychotropic drugs.

At baseline (Visit 2), patients who continue to meet all eligibility criteria will be randomly assigned to 1 of the 2 treatment arms for a 6-week, double-blind treatment period. Patients will be randomly assigned to 1 of the following groups: 60 mg ITI-007 or matching placebo.

Double-Blind On-Treatment Period (6 Weeks)

Patients will take their first dose of study medication the evening of their baseline visit. A single dose will be taken each day in the evening, with or without food, for the duration of the 6-week On-treatment Period.

Following randomization, patients will attend the clinic on Days 8, 15, 22, 29, 36 and 43.

Safety Follow-up Period (2 Weeks)

A return to the clinic for a safety follow-up visit will occur at Week 8, approximately 2 weeks following the last dose of study medication. If possible, patients who withdraw prematurely will be seen for an early termination visit (within 1 week of early termination) and will be asked to return to the clinic for a safety follow-up visit 2 weeks following withdrawal.

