5 STUDY ENROLLMENT AND WITHDRAWAL

5.1 Patient Inclusion Criteria

Each patient must meet all of the following criteria to be enrolled in this study:

- 1. Is capable of understanding the written informed consent, provides signed and witnessed written informed consent, and agrees to comply with protocol requirements.
- 2. Is between the ages of 18 and 75 years, inclusive, at the start of screening (both male and female patients are to be included).
- Meets the Diagnostic and Statistical Manual of Mental Disorder, 5th Edition (DSM-5) criteria for Bipolar I or Bipolar II Disorder as confirmed by the investigator or sponsor-approved expert site-based rater by a M.I.N.I. International Neuropsychiatric Interview and meeting all of the following 5 criteria:
 - a. The start of the current MDE is at least 2 weeks but no more than6 months prior to the screening visit;
 - b. Appropriate severity of illness, at least moderately ill, as measured by a rater-administered MADRS total score ≥20 and corresponding to a CGI-BP-S score of ≥4 at the screening and baseline visits;
 - c. Sufficient history and/or independent report (such as family member or outside practitioner) verifying that the current MDE is causing clinically significant distress or impairment in social, occupational, or other important areas of functioning;
 - A lifetime history of at least 1 Bipolar manic episode or mixed episode (for Bipolar I) or hypomanic episode (for Bipolar II);
 - e. A rater-administered YMRS total score of ≤12 at the screening and baseline visits.
- 4. Has a body mass index (BMI) of 19 35 kg/m², inclusive.
- 5. Either must agree to use highly effective methods of birth control (defined as those, alone or in combination, that result in a failure rate less than 1 percent per year when used consistently and correctly) for at least 2 weeks prior to randomization (starting with signing informed consent) through to the end-of-study follow-up visit or must be of non-childbearing potential (defined as either permanently sterilized or, if female, post-menopausal; the latter is defined as at least 1 year with no menses without an alternative medical explanation).

6. In the opinion of the investigator, the patient is willing and able to comply with study requirements, study visits, and to return to the clinic for follow-up evaluations as specified by the protocol.

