- 5. Patients who have experienced hallucinations, delusions, or any other psychotic symptomatology in the current depressive episode may be allowed as long as these symptoms are not attributable to a primary DSM-5 diagnosis other than Bipolar Disorder as described in exclusion number 4. The presence of these symptoms should be reviewed with the Medical Monitor and the adjudication team on a case by case basis prior to inclusion. Patients with YMRS of >12 will be reviewed on a case by case basis to rule out possible impending mania/hypomania.
- The patient has been hospitalized for mania associated with Bipolar I Disorder within 30 days of screening.
 Note: This criterion is included to ensure that any manic phase has completely resolved before enrollment in the study.
- 7. The patient has received electroconvulsive therapy, vagal nerve stimulation, or repetitive trans-cranial magnetic stimulation within the last 5 years or received more than 1 course of electroconvulsive therapy during the patient's lifetime.
- 8. The patient is considered a rapid cycler, defined by the occurrence of at least 6 major depressive, manic, hypomanic, or mixed episodes during the previous year. These episodes must be demarcated either by a partial or full remission of at least 2 months' duration or by a switch to an episode of opposite polarity. (Each MDE must have lasted at least 2 weeks, each manic or mixed episode must have lasted at least 1 week, and each hypomanic episode must have lasted at least 4 days, as validated by a reliable informant). Note: This criterion is included to avoid spontaneous remission during participation in the study that might confound treatment results.
- 9. The patient is considered treatment-resistant, defined as having a lifetime history of treatment resistance (no remission) to ≥2 treatments with medications approved by the regional regulatory authority for Bipolar Depression [which may include, for example, lurasidone, quetiapine or Symbyax (olanzapine/fluoxetine combination), depending on the region] at an adequate dose (per regulatory-approved label) for an adequate duration (at least 6 weeks).
- 10. The patient is currently receiving formal cognitive or behavioral therapy, systematic psychotherapy, or plans to initiate such therapy during the study.

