8.1.8 Young Mania Rating Scale

The YMRS is an 11-item, clinician-administered mania rating scale with established reliability, validity, and sensitivity that was designed to assess the severity of manic symptoms (Young et al 1978). Four of the YMRS items are rated on a 0 to 8 scale, with the remaining 7 items rated on a 0 to 4 scale. The total score is appropriate both for assessing baseline severity of manic symptoms and for assessing treatment-emergent manic symptoms in patients with Bipolar I or Bipolar II Disorder with Depression. It will

be completed by the investigator or an expert site-based rater according to Appendix A (Schedule of Events).

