Patients who discontinue study or study drug due to AEs will be listed and summarized by system organ class and preferred term. TEAEs will be categorized to monitor signals of potential abuse of ITI-007 and the number and percentage of patients with at least one abuse-related TEAE will be summarized by the pre-specified categories.

Additional summaries of TEAEs will be presented as deemed necessary and will be specified in the SAP.

Laboratory assessments, including hematology and chemistry, vital signs and ECGs, will be listed and summarized by treatment group and visit. Summaries may include actual and change from baseline, incidence of abnormal values according to normal range criteria, shift from baseline to each visit according to markedly abnormal criteria, and listing of patients meeting certain abnormal criteria. Pre -specified chemistry results, including but not limited to blood levels of fasting glucose, total cholesterol, triglycerides, and insulin will be evaluated for whether there is a difference between ITI-007 and placebo. Any comparison between the treatment groups will be considered exploratory.

The observed and change from baseline in the scores of the different rating scales (YMRS, C SSRS, AIMS, BARS, and SAS) will be summarized by treatment group and visit.

Additional details for analyses on safety assessments will be provided in the SAP.

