3.2.3. SAFETY SECONDARY OBJECTIVES

The safety secondary objectives of this study are to determine the safety and tolerability of lumateperone, administered orally once daily for 6 weeks in subjects with Bipolar Depression, compared to placebo. Safety and tolerability will be assessed in relation to:

- Incidence of adverse events (AEs);
- Mean change from baseline in the Young Mania Rating Scale (YMRS);
- Mean change from baseline in the Columbia Suicide Severity Rating Scale (C-SSRS);
- Mean change from baseline in the Abnormal Involuntary Movement Scale (AIMS);
- Mean change from baseline in the Barnes Akathisia Rating Scale (BARS);
- Mean change from baseline in the Simpson Angus Scale (SAS);
- Changes from baseline in clinical laboratory evaluations;
- Changes from baseline in electrocardiograms (ECGs);
- Changes from baseline in vital sign measurements;
- Physical and neurological examination findings.

Document: Author:

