16.6.3. ABNORMAL INVOLUNTARY MOVEMENT SCALE (AIMS)

The AIMS is a clinician rated assessment of abnormal movements. It contains items related to: facial and oral movements; extremity movements; trunk movements; global judgments and dental status. Seven items of the AIMS range from 0= "None" to 4= "Severe". A score of "mild" (2) in two or more categories or a score of "moderate" or "severe" in any one category results in a positive AIMS score (i.e. the scores are not averaged). The global severity score is the response to "Severity of abnormal movements" found within the global judgments section. Additionally, overall severity is scored on the basis of severity of abnormal movements and incapacitation due to abnormal movements.

The (non-global) AIMS total score is the sum of items 1 through 7. The possible range for the AIMS total score is 0 to 28. Higher values of the total AIMS score indicate increased severity in abnormal movement. If one or more of the AIMS total score items are missing at a visit, the score will be set to missing.

The observed and change from baseline in AIMS total scores to Day 43 will be summarized by treatment.

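### The only rating-based mania analysis is YMRS value and change, which is insensitive to switches in a few patients; no count of emergent cases by arm is planned

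*SAP*

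**What the plan says.** The safety objective in SAP 3.2.3, as in Protocol 3.1.2.3, lists "Mean change from baseline in the Young Mania Rating Scale (YMRS") as one item, separate from the incidence of adverse events. Protocol 8.1.8 calls the YMRS total suitable "for assessing treatment-emergent manic symptoms in patients with Bipolar I or Bipolar II Disorder with Depression", and SAP 16.6.1 repeats this. The analysis that follows in SAP 16.6.1 is: "The observed and change from baseline in YMRS total score will be summarized by treatment and visit". The safety text in Protocol 12.4.4 plans the same for all the scales: "The observed and change from baseline in the scores of the different rating scales". The heading of SAP 16.1 adds a last on-treatment value, cut off one day after the final dose.

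Two eligibility passages mention a YMRS of 12. Inclusion 3e requires "A rater-administered YMRS total score of ≤12 at the screening and baseline visits". Exclusion 5 says "Patients with YMRS of >12 will be reviewed on a case by case basis to rule out possible impending mania/hypomania".

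For AIMS, SAP 16.6.3 states which item pattern "results in a positive AIMS score (i.e. the scores are not averaged"), but the only output it then names is the total score and its change to Day 43.

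**The concern.** In bipolar depression, the mania question is largely about individuals: does a patient move from depression into mania or hypomania? That matters here because Protocol 5.2 and 6.6 require patients to come off psychotropic drugs, including mood stabilizers. A mean answers a different question. If most patients stay low or drift lower, a few large rises are diluted.

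The SAP already counts patients for other risks:

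- emergence of suicidal ideation and behavior (16.6.5);
- extrapyramidal TEAEs by MedDRA query (16.1.3);
- markedly abnormal laboratory, ECG and vital-sign values (16.2.1, 16.3.1, 16.4.1).

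No such count is visible for the YMRS, although Protocol 9.1.2 has it rated at screening, baseline and each later scheduled visit. At stake is whether the report can say, from ratings, how many patients in each arm developed manic symptoms.

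**Working it through.** **The plan's own figures.** There is none for YMRS change or switch rate. The YMRS range checks: 4 × 8 + 7 × 4 = 60. The arm size comes from Protocol 12.1: 163 evaluable per arm, difference 3, SD 9.0 and two-sided 0.05 give 85.3% power against the stated 85%. Randomizing 350 patients 1:1 gives 175 per arm.

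**Assumed inputs (not in the documents).** Switch rates p, a rise J of 10 to 15 points in a switcher, and an SD of 3 to 5 for YMRS change in other patients.

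**Step 1. Effect on the mean: 3% excess, J = 15, no placebo switches, 163 per arm.**

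- Shift = 0.03 × 15 = 0.45 points.
- Switchers add variance to their arm: 0.03 × 0.97 × 15² = 6.55.
- SE = √[(2 × SD² + 6.55) / 163].

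| SD | SE | z = 0.45 / SE |
|---|---|---|
| 3 | 0.39 | 1.16 |
| 4 | 0.49 | 0.93 |
| 5 | 0.59 | 0.76 |

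With 175 per arm, z is 0.79 to 1.20. The 0.45 assumes that all switchers are elevated at the same visit; if they are spread over six visits, each by-visit mean moves less.

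**Step 2. Power of the mean and of the proportion, 175 per arm, two-sided 0.05.** For the mean, the shift is (p1 − p0) × J, the variance in each arm is SD² + p(1 − p)J², and power = Φ(shift/SE − 1.96). Example with 5% versus 1%, J = 15 and SD 4: shift 0.60; SE = √[(26.69 + 18.23)/175] = 0.507; power = Φ(1.18 − 1.96) = 22%. The exact column sums the binomial probabilities of all count pairs in the direction of harm with a two-sided Fisher p of at most 0.05.

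| Switch rates | Expected patients | Mean shift | Power, mean | Power, proportion (normal approx.) | Power, proportion (Fisher) |
|---|---|---|---|---|---|
| 3% vs 1% | 5 vs 2 | 0.2 to 0.3 | 6% to 12% | 27% | 13% |
| 5% vs 1% | 9 vs 2 | 0.4 to 0.6 | 10% to 30% | 59% | 48% |
| 8% vs 1% | 14 vs 2 | 0.7 to 1.05 | 23% to 63% | 89% | 88% |

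**Step 3. Masking.** If 95% of an arm improve by 1.5 points and 5% rise by 15, the mean change is 0.95 × (−1.5) + 0.05 × 15 = −0.7. The arm still looks improved.

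**Step 4. Limit of the count.** For 5/175 versus 0/175, the two-sided Fisher p is 2 × C(175,5)/C(350,5) = 0.061. A count makes the cases visible; it does not make a small excess conclusive.

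**The case against.** A reader might infer that mania is assessed by mean YMRS change alone. The documents do not support that:

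- A switch can be reported as an adverse event, since Protocol 9.1.10.1 covers both new illness and worsening of the treated condition. SAP 16.1.1 compares TEAEs by arm for each preferred term, with relative risk, interval and p-value.
- SAP section 8 includes the maximum in continuous summaries, and Protocol 12.4 lists safety data for all treated patients. The protocol's safety text also allows out-of-range values to be flagged and tabulated where appropriate.
- CGI-BP-S has a mania subscale. SAP 15.4.1 on subscale scores appears in the contents, but its text is not visible, and neither are the table shells.

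These points narrow the concern but leave the gap. TEAE tables depend on investigator reporting and spread manic events over separate terms. The only visible grouping with elevated-mood terms is the abuse category in SAP 16.1.4, and SAP Table B separates adverse-event discontinuations only by whether they reflect worsening depression. A maximum is one value per arm and visit, not a number of patients. The title of SAP 15.4.1 refers to change scores.

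A reader might also infer that ratings made after stopping drug are lost, because "patients who withdraw prematurely will be seen for an early termination visit (within 1 week of early termination"), while the last on-treatment value ends one day after the final dose. That limit governs only that value. SAP section 7, Table A, maps early-discontinuation visits to target days, so such a rating can enter the by-visit table. It may still be displaced when another rating in the same window lies closer to the target day.

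Finally, the AIMS gap is softened by the extrapyramidal TEAE counts in SAP 16.1.3, but those do not use the AIMS rating.

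**Conclusion.** The point holds as a cheap improvement. In the visible text, the mania ratings are analysed only as observed value, change and a last on-treatment value, and no patient-level emergence count by arm is planned. With a 3% excess, a mean shift of about half a point sits near one standard error. That size rests entirely on assumed switch rate, rise and SD. The count gains clear power over the mean at 5% or 8% versus 1%; at 3% versus 1% the exact gain is small and the benefit is mainly that cases are seen.

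Two further inferences should be resisted. It is not established that everyone enters at 12 or less, because exclusion 5 leaves review of patients above 12 open while inclusion 3e does not. Nor is a score above 12 an on-treatment warning level; the documents use it only for eligibility. No primary or key secondary inference is affected.

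**What to change.** - **SAP 16.6.1:** among patients with baseline YMRS of 12 or less, report by arm how many, and what percentage, exceed a cut-off at any post-baseline visit through Day 43 or the early termination visit. Include early-termination ratings made off drug. Give the risk difference with a 95% CI, and show the table beside a grouped set of mania/hypomania TEAE terms.
- **Cut-off:** the sponsor fixes it before unblinding. Above 12, the entry limit, is one option; a move from 12 to 13 would then count the same as a full switch.
- **Protocol 5.1 and 5.2:** inclusion 3e and exclusion 5 must be reconciled on entry above 12.
- **SAP 16.6.3:** report by arm the number with a positive AIMS score post-baseline among those not positive at baseline, using the existing definition.

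The cost is two small tables from data already collected. Protocol section 12 lets the SAP change analysis methods without an amendment. The drawback is small counts with wide intervals, so both tables should be labelled descriptive.

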16.6.2. BARNES AKATHISIA RATING SCALE (BARS)

The BARS is a rating scale, measuring the observable, restless movements that characterize akathisia. It consists of 4 items: objective restlessness, awareness of restlessness, distress related to restlessness and global clinical assessment of akathisia. Each item is on a 4-point scale (0 to 3), except for the global clinical assessment which is on a 6-point scale (0 to 5), both using low values to represent absence of akathisia and high representing severe akathisia. The BARS total score is the sum of items 1 through 3 and ranges from 0 to 9. Higher values of the BARS total score indicate akathisia is higher in severity. If one or more items at a visit are missing the total will not be calculated.

The observed and change from baseline in BARS total scores to Day 43 will be summarized by treatment.

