5.5.2 Handling of Patient Withdrawals or Patient Discontinuation of Study Intervention

Patients are free to withdraw from the study or study treatment at any time. Patient participation in the study may be stopped at any time at the discretion of the investigator or at the request of the sponsor.

Patients who discontinue study treatment or active participation in the study will no longer receive study treatment. When a patient withdraws from the study, the reason(s) for withdrawal shall be recorded by the investigator on the relevant screen of the electronic case report form (eCRF). Whenever possible, all patients who discontinue study treatment or withdraw from the study prematurely will undergo all end-of-study assessments. Patients who fail to return for final assessments will be contacted by the study site (2 documented telephone calls followed by 1 registered letter or similar procedures depending on regional differences) in an attempt to have them comply with the protocol.

It is vital to obtain follow-up data on any patient withdrawn as a result of an AE or serious AE (SAE). In every case, efforts must be made to undertake protocol-specified, safety, follow-up procedures. All data collected from all patients, including early withdrawals, will be used in the reporting and analysis of the study.

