16. SAFETY OUTCOMES

All outputs for safety outcomes will be based on the SAF Set.

16.1. FOR BY VISIT SUMMARIES OF CHANGE FROM BASELINE SUMMARIES, THE LAST VALUE ON TREATMENT (LAST ASSESSMENT ON OR BEFORE THE LAST DOSE OF STUDY MEDICATION PLUS ONE DAY) WILL BE PRESENTED. ADVERSE EVENTS

Adverse Events (AEs) will be coded using the Medical Dictionary for Regulatory Activities

Document: ...\ITI\ITI-007\MYA11638\Biostatistics\Documentation\SAP\ITI-007-404 SAP Final V1.0 12JUN2019.docx
Author: Version Number:1.0

Version Number:1.0
Version Date: 12JUN2019

Page 31 of 53

(MedDRA) central coding dictionary currently in effect at the time of analysis or database lock.

Treatment emergent adverse events (TEAEs) are defined as AEs that started or worsened in severity on or after the first dose of study medication and on or before the date last dose of study medication plus one day.

All AEs with an onset date after the last dose of study medication plus one day will be listed in the AE data listing and labelled as 'Follow-up Adverse Event'.

See APPENDIX 2 for handling of partial or completely missing dates for AEs. In the case where it is not possible to define an AE as treatment emergent or not due to missing dates, the AE will be classified as the worst case, i.e. treatment emergent.

An overall summary of number of subjects within each of the categories described in the subsections 16.1.1 and 16.1.2 below will be provided as specified in the TLF shells.

Listings will include all AEs, TEAEs and Non-TEAEs. A seperate listing for TEAEs leading to study discontinuation will be presented.

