16.6.4. SIMPSON-ANGUS RATING SCALE (SAS)

The SAS is a measure of extrapyramidal side effects consisting of 10 items: gait, arm dropping, shoulder shaking, elbow rigidity, wrist rigidity, head rotation, glabella tap, tremor, salivation and akathisia. Items are rated on a scale from 0 (normal) to 4 (extreme in severity). The SAS total score is defined as the sum of all 10 items and ranges between 0 and 40. Lower values of the SAS total score indicate milder symptoms. If one or more items are missing at a visit the SAS total score will be set to missing.

The observed and change from baseline in SAS total scores to Day 43 will be summarized by treatment.

Document: ...\ITI\ITI-007\MYA11638\Biostatistics\Documentation\SAP\ITI-007-404 SAP Final V1.0 12JUN2019.docx Author: Version Number:1.0

Version Data

Page 41 of 53

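### The SAP summarizes BARS, AIMS and the Simpson-Angus Scale as change to Day 43 without the by-visit summary in Protocol 12.4.4, so as written these scale tables leave out early-termination scores from before day 40

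*SAP*

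**What the plan says.** The three movement scales share one form of words in the SAP:

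- BARS (SAP 16.6.2): "The observed and change from baseline in BARS total scores to Day 43 will be summarized by treatment".
- AIMS (SAP 16.6.3): "The observed and change from baseline in AIMS total scores to Day 43 will be summarized by treatment".
- Simpson-Angus Scale (SAP 16.6.4): "The observed and change from baseline in SAS total scores to Day 43 will be summarized by treatment".

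SAP 16.6.1, just before these, has the YMRS summarized by treatment and visit. Protocol 12.4.4 makes no distinction among the five scales: "YMRS, C SSRS, AIMS, BARS, and SAS) will be summarized by treatment group and visit".

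Protocol 5.5.2 asks that, where possible, patients who stop early "will undergo all end-of-study assessments". It adds that data from early withdrawals will be used in reporting and analysis. Protocol 4 sets the timing: such patients, if possible, "will be seen for an early termination visit (within 1 week of early termination").

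One general sentence on safety summaries has run into the heading of SAP 16.1. It opens by limiting itself to by-visit summaries of change from baseline, and then says: "THE LAST VALUE ON TREATMENT (LAST ASSESSMENT ON OR BEFORE THE LAST DOSE OF STUDY MEDICATION PLUS ONE DAY) WILL BE PRESENTED".

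**The concern.** Mean changes in AIMS, BARS and the Simpson-Angus Scale are named safety objectives in both documents, and the Protocol's background section presents low extrapyramidal liability as an expected property of the drug. A summary at Day 43 alone describes patients who were still being assessed at Day 43. Anyone who stopped earlier, for whatever reason, contributes nothing to it, even when a rater completed the scale at the termination visit. If movement effects lead some patients to stop, the scale summary would be the output least able to show it. The SAP is also narrower here than the Protocol, and the visible SAP text neither says that this is a change nor gives a reason.

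**Working it through.** There is no stated figure to reproduce. The check is a comparison of texts followed by a trace through the visit windows.

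**1. SAP against Protocol**

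| Scale | Protocol 12.4.4 | SAP |
|---|---|---|
| YMRS | by treatment and visit | by treatment and visit (16.6.1) |
| BARS | by treatment and visit | to Day 43, by treatment (16.6.2) |
| AIMS | by treatment and visit | to Day 43, by treatment (16.6.3) |
| Simpson-Angus | by treatment and visit | to Day 43, by treatment (16.6.4) |

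**2. Where an early-termination score goes.** SAP Section 7 maps early discontinuation visits through Table A: relative days 2–11 to Day 8, 12–18 to Day 15, 19–25 to Day 22, 26–32 to Day 29, 33–39 to Day 36, and 40 onward to Day 43. An assessment before day 40 therefore never carries the Day 43 label.

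Assume that termination is dated at the last dose and that the visit follows within 7 days.

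- Last dose on day 12: the visit falls on days 12 to 12 + 7 = 19 and is mapped to Day 15 or Day 22.
- Last dose on day 32: the latest visit is 32 + 7 = 39, mapped to Day 36. So no termination visit held within the week after a last dose on or before day 32 reaches the Day 43 window.
- Last dose on days 33 to 39: the visit may or may not reach it.

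**3. Whether the last-on-treatment sentence recovers the score.** There are two obstacles.

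- Scope: the sentence is worded for by-visit summaries, which SAP 16.6.2–16.6.4 do not specify. The laboratory section (SAP 16.2) states a last on-treatment summary itself; the three scale sections do not.
- Timing: it accepts values up to the last dose plus one day. With a last dose on day 12 the limit is day 13, so a termination visit on days 14 to 19 falls outside it.

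**4. Possible scale.** No dropout rate to Day 43 is given. The only attrition figure, 10% in Protocol 12.1, concerns loss before the first post-dose MADRS. For an assumed 10% to 25% stopping before the Day 43 window:

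- 0.10 × 350 = 35 patients (17.5 per arm)
- 0.25 × 350 = 87.5, about 88 patients (43.75, about 44 per arm)

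These are patients without a Day 43 score for any reason, not patients with movement symptoms. How many have an earlier score to recover cannot be computed, because the schedule of events (Protocol Appendix A) is not in the available text.

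**The case against.** The strongest reply is that the safety analysis as a whole does not lose these patients. On the Safety Analysis Set they count in the extrapyramidal event tables under the narrow and broad MedDRA queries (SAP 16.1.3), in adverse event incidence and relative risk and in events leading to discontinuation (SAP 16.1.1), and in the time-to-discontinuation analysis (SAP 9). None of these depends on reaching Day 43. This stands. A reader might infer that patients who stop for akathisia vanish from the movement-disorder results, and the documents do not support that.

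Second, the wording may mean through Day 43. SAP 16.4 describes change in vital signs to Day 43 and then presents every visit. SAP 8 leaves table content to shells that are not in the available text. This stands as an ambiguity. It does not settle the matter, because SAP 16.4 names each visit expressly and 16.6.2–16.6.4 do not.

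Third, Protocol 12.4 lets the SAP state otherwise on summaries by time point, and Protocol 12 lets it change methods without an amendment. So it is too strong to say that the Protocol's by-visit summary binds the SAP. Protocol 12 does, however, expect changes to be documented, and none is visible here, although parts of the SAP are blacked out.

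Fourth, if Appendix A schedules these scales after baseline only at Day 43 or early termination, by-visit tables add little. That is so, but the termination score would then be an early stopper's only post-baseline value, and including it would matter more.

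Fifth, the one-day limit is a coherent on-treatment rule that matches the adverse event window. Agreed. The proposal keeps it and adds a second row beside it.

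**Conclusion.** The point holds as a gap in the rating-scale summaries. SAP 16.6.2–16.6.4 are narrower than Protocol 12.4.4 and than the SAP's own YMRS section. Followed literally, they omit scores from patients last assessed before day 40, and the last-on-treatment sentence does not clearly bring them back.

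The size is known only by construction: no early-termination score before day 40 enters the Day 43 summary. The count of 35 to about 88 patients rests on an assumed dropout range and on reading the wording as Day 43 alone. A reader might go further and infer a bias in favour of one arm. The documents give neither discontinuation by arm nor movement-scale changes, so neither the direction nor the size of a bias can be stated.

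This concerns a named safety objective and is worth correcting before unblinding. It does not touch the primary or key secondary analysis.

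**What to change.** In SAP 16.6.2–16.6.4:

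1. Summarize observed values and change by treatment and by each visit at which the scale is done.
2. Add the last on-treatment value, with the existing limit of last dose plus one day.
3. Add a last post-baseline row that includes early-termination assessments, and flag those taken more than one day after the last dose.

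Move the displaced sentence out of the SAP 16.1 heading into the body of Section 16, and say that it covers these scales.

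Optional: SAP 16.6.3 defines what "results in a positive AIMS score (i.e. the scores are not averaged") but states no output that uses it. A count by arm of patients newly positive after baseline would use that definition. No document promises such a table, so this is a preference.

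The cost is SAP wording and a few more table rows from data already collected. The drawback is that some last values are taken off drug, which is why the two last-value rows should stay separate and the later values be flagged.
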